Study Design	Part 2 - AGI-134 at the RP2D
	This part is designed to assess the safety, tolerability and biological activity of AGI-134 at the RP2D in subjects with either deep or superficial unresectable/metastatic solid tumours.
	Subjects with selected unresectable/metastatic solid tumours, either superficial or deep lesions  , will be enrolled and receive intratumoural injections of AGI-134 according to the injected tumour dimensions, and for a maximum of the RP2D at each dosing, every three weeks for up to 4 cycles.
Study Assessments	This is a two-part study. Each part will comprise of a screening period, a Core study, and a Long-Term Follow-Up period. Details of assessments to be done at each visit are provided within the protocol and the Schedule of Assessments (SoA) (ref to APPENDIX A).
	Visit Requirements
	Screening Visit
	A window of 28 days is allowed for the Screening period procedures, from the time of Informed Consent Form (ICF) signature until Baseline visit, with the exception of all safety laboratory assessments (CBC, biochemistry, coagulation test), which should be completed within 10 days prior to treatment initiation. Eligibility information will be sent to the Sponsor for review and approval prior to subject's entry into the study.
	Subjects who fail the Screening procedures may be rescreened after consultation with the Sponsor. Rescreening should include procedures listed in Section 5.1, including re-consent signature.
	Baseline Visit
	The Baseline visit should occur up to 28 days from the Screening visit. Only subjects who fully comply with the Inclusion/Exclusion Criteria for the study will be eligible for participation and will undergo Baseline visit activities. Treatment initiation (Day 1 visit activities) may be done on the same day of the Baseline, but Baseline procedures should be completed prior to investigational product administration.

<sup>1 Deep lesions are defined as non-palpable lesions, including but not limited to subcutaneous lymph nodes or visceral lesions, injectable with ultrasound or CT guidance. The deep lesions should not be encasing or abutting major vascular structure, e.g., peri-aortic or peri-carotid lesions, or be in a location that is considered high risk for adverse events, e.g., pulmonary parenchyma lesions.

agalin A subsidiary of Bit	OLINERX	PRIVILEGED & CONFIDENTIAL
Investigational Product: AGI-134		Protocol No. AGI-134.FIM.101

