# Investigational Product Route and Dosage Form

The investigational product in this study is AGI-134. The drug is provided as a 25 mg/mL sterile dispersion in phosphate buffered saline (PBS).

In the dose escalation phase, AGI-134 will be administered by intralesional injection at escalating total doses of 25 mg (1 mL), 50 mg (2 mL), 100 mg (4 mL) and up to 200 mg (8 mL) in 3-week cycles until progression, toxicity or 4 cycles completion, whichever comes first. The total volume of the AGI-134 injection may be divided to more than one lesion while maintaining a minimum of 1 mL per injection site. In Part 2 of the study, the treatment schedule will be the same, and the dose of AGI-134 used will be according to the lesion dimensions and up to the RP2D.

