#### Part 2:

- a) After 3 subjects with deep injectable lesions (or 6 subjects, if expansion is needed) have completed the first cycle of treatment with AGI-134 (i.e. Cycle 1/Day 1 through to Day 21).
- b) Every 6 months to review ongoing safety data until the last patient last visit (LPLV).

During this part, 3 subjects will be evaluated after one cycle of injection into a deep lesion. If one or more of the subjects' experiences DLTs, a new assessment will be done after additional 3 subjects with deep lesions injected are enrolled and treated (total of 6 subjects). If no new DLTs are reported, the recruitment will continue as planned. If 2 or more subjects presented a DLT, the Safety Committee will assess the risk vs. benefit of the treatment and recommend whether or not the dose of AGI-134 should be reduced and/or the treatment schedule be changed (see Section 8.3: Ongoing Safety Assessment and Dose-Limiting Toxicity).

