### 3.1.1 Ongoing Safety Assessment and Dose-Limiting Toxicity

AEs will be reported from the time of informed consent signature up to 30 days after the last dose of study drug or until the initiation of new anti-cancer treatment, whichever is sooner. SAEs will be reported until 90 days after the last dose of study drug, or until the initiation of new anti-cancer treatment, whichever is sooner. The period considered for DLT assessment for Part 1 is defined as the time from the first dose administration of AGI-134 and up to the end of the first cycle of therapy (i.e. Cycle 1/Day 1 to Cycle 1/Day 21).

agalin A subsidiary of BIG	PRIVILEGED & CONFIDENTIAL
Investigational Product: AGI-134	Protocol No. AGI-134.FIM.101
Phase: I/IIa	Version 6.1 31 May 2021

The period considered for DLT assessment for Part 2 is defined as the time from the first dose administration of AGI-134 and up to the end of the first cycle of therapy (i.e. Cycle 1/Day 1 to Cycle 1/Day 21) for the first 3 subjects with deep lesions.

After the DLT assessment period, data will be assessed on an ongoing basis during the study. All AEs should be captured within the eCRF, however AEs reported beyond the DLT period will not be considered for the DLT assessment.

During Part 2 of the study, any specific AE that fits the DLT definition and occurs at a frequency of > 30% will stop accrual. In this scenario, the Safety Committee may recommend a lower dose level or dosing schedule change for the continuation of the expanded cohort. The study will be discontinued or terminated in case of an unacceptable risk or a negative change in the risk/benefit assessment. This might include the occurrence of adverse events for which character, severity or frequency is unexpected and overcome the potential benefit of the study drug. In addition, any data deriving from other clinical trials or toxicological studies which negatively influence the risk/benefit assessment might cause discontinuation or termination of the study.

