# 8.3 Ongoing Safety Assessment and Dose-Limiting Toxicity

AEs will be reported from the time of informed consent signature and up to 30 days after the last dose of study drug or until the initiation of new anti-cancer treatment, whichever is sooner. SAEs will be recorded up to 90 days following the last dose of study drug or until the subject initiates new anti-cancer therapy, whichever is earlier.

The period considered for dose-limiting toxicity (DLT) and safety assessment for the accelerated escalation is defined as the time from the first dose administration of AGI-134 and up to the end of the first cycle of therapy (i.e. Cycle 1 - Day 1 through Cycle 1 - Day 21). Data will be reviewed by the Safety Committee. The Safety Committee will be composed of the Study PI together with the Sponsor's MM and Pharmacovigilance Manager (PhV) or designee which will be responsible for the review of all the safety data at pre-defined time points during Part 1 and 2. Safety will be monitored throughout the study.

Beyond the DLT assessment period, data will be assessed continually on an ongoing basis. AEs reported beyond the DLT assessment period will be captured within the eCRF, however will not be considered for DLT assessment period. During Part 2 of the study, any specific AE that fits the DLT definition, occurring at a frequency of >30% will stop accrual. In this situation, the Safety Committee may recommend a lower dose level or dosing schedule change for the continuation of AGI-134 at the RP2D.

Sites will be required to contact the Sponsor within 24 hrs if subjects present with an AGI-134 related AE that is moderate or higher grade and clinically significant or experience DLTs during the DLT assessment period (see Section 3.1.1).

A subject that dropped out of the study will be included in all relevant data analyses and presentation as described in the statistical section.

20		PRIVILEGED & CONFIDENTIAL
Investigational Product: AGI-134	A Phase I/IIa, multicentre, two-parts, open label study designed to evaluate the safety and tolerability of escalating	Protocol No. AGI-134.FIM.101
Phase: I/IIa		Version 6.1 31 May 2021

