### 8.3.2 Part 2 - AGI-134 at the RP2D

Safety interim analyses are planned after 3 subjects with deep injectable lesions have completed the first cycle with AGI-134 (i.e. Cycle 1 - Day 1 through to Cycle - Day 21). Sites will be required to contact the Sponsor within 24 hrs if a subject present with a DLT during the DLT assessment period (see Section 3.1.1).

During Part 2, 3 subjects will be evaluated after one cycle of injection into deep lesions. If one or more of the subjects experiences DLTs, a new assessment will be done after the additional 3 subjects with deep lesions injected are enrolled and treated (total 6 subjects). If no new DLTs are reported, the recruitment will continue as planned. If 2 or more subjects presented a DLT, the SC will assess the risk vs. benefit of the treatment and recommend whether or not the dose of AGI-134 should be reduced and/or the treatment schedule be changed (see Section 8.3).

Following the assessment of the first 3 patients with deep lesion injected or 6 patients if expansion is needed, the safety data will be evaluated by the Safety Committee. Evaluation by

agalin A subsidiary of Bio	nnune DLINERX	PRIVILEGED & CONFIDENTIAL
Investigational Product: AGI-134		Protocol No. AGI-134.FIM.101
Phase: I/IIa		Version 6.1 31 May 2021

the Safety Committee will be conducted every 6 months to review ongoing safety data, until the last patient last visit (LPLV).

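### If the RP2D exceeds 25 mg, the Part 2 deep-lesion run-in can clear with no subject having received the RP2D in a deep lesion, and Section 3.1.1 words the Part 2 DLT period too narrowly

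*Combined protocol and SAP*

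**What the plan says.** **Aim and dose.** The Synopsis (Study Design) describes Part 2 as assessing safety, tolerability and "biological activity of AGI-134 at the RP2D in subjects with either deep or superficial unresectable/metastatic solid tumours". Under Investigational Product Route and Dosage Form it states that "the dose of AGI-134 used will be according to the lesion dimensions and up to the RP2D". Section 3 (Part 2) and Section 6.7.4 agree that the RP2D is a cap. Section 3 also lets the investigator use one or more tumours.

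**Lesions.** Section 4.1, criterion 7, asks that a Part 2 tumour accept at least 1 mL. The same criterion requires the full cohort volume in Part 1, but criterion 4 limits Part 1 injection to superficial or palpable tumours.

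**Run-in.** Section 3.1 (Part 2) says "3 subjects will be evaluated after one cycle of injection into a deep lesion", and Section 8.3.2 says "Safety interim analyses are planned after 3 subjects with deep injectable lesions have completed the first cycle with AGI-134". Any DLT leads to three more deep-lesion subjects. With no new DLT, recruitment goes on. With DLTs in two or more subjects, the Safety Committee weighs risk against benefit and advises on dose or schedule. Section 9.7 repeats this.

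**Contact and review rules.** Section 8.3.2: "Sites will be required to contact the Sponsor within 24 hrs if a subject present with a DLT during the DLT assessment period". Section 8.3 has sites "contact the Sponsor within 24 hrs if subjects present with an AGI-134 related AE that is moderate or higher grade", if clinically significant, in the same period. It adds: "Beyond the DLT assessment period, data will be assessed continually on an ongoing basis". A specific AE that fits the DLT definition and exceeds 30% frequency stops Part 2 accrual.

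**DLT period.** Section 3.1.1 gives the Part 2 period as Cycle 1, Day 1 to Day 21, "for the first 3 subjects with deep lesions". The Synopsis gives the same period for Parts 1 and 2 without that restriction.

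**The concern.** The run-in is the only planned early check of injection into deep lesions. Its result will naturally be read as support for the RP2D in deep lesions, because that is how Part 2 is titled and described. The written rule counts DLTs in subjects whose deep-lesion dose may be well below the RP2D. Part 1 cannot fill the gap, since it provides no deep-lesion data at any dose.

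At stake is what the Committee's clearance means. After a low-dose run-in, the first deep injection at or near the RP2D could fall to a later subject, with nothing in the supplied text marking that step. That later subject is also one for whom the wording of Section 3.1.1 leaves DLT coverage unclear.

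**Working it through.** **1. The plan's figures.** At 25 mg/mL, volumes of 1, 2, 4 and 8 mL give 25, 50, 100 and 200 mg, as the Synopsis states. The documents give no operating characteristic for the run-in, so there is none to reproduce.

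**2. Lowest dose the text allows.** 1 mL × 25 mg/mL = 25 mg. This comes from an eligibility criterion; it is not a stated minimum or typical dose. As a share of each possible RP2D:

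| RP2D (mg) | 25 / RP2D |
|---|---|
| 25 | 1 (no gap) |
| 50 | 1/2 |
| 100 | 1/4 |
| 200 | 1/8 |

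**3. Search for a dose condition.** Three places could hold one. The run-in triggers (Synopsis; Sections 3.1, 8.3.2, 9.7) refer to subjects, a cycle and DLTs. The DLT definition (Section 8.3.3) needs only one dose of any size. The replacement rule (Section 4.5) depends on withdrawal. None requires a run-in subject to have received the RP2D, or any share of it, in a deep lesion. The number who did can therefore be 0 of 3 or 0 of 6 at clearance. That is the permitted extreme, not an expected value.

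**4. What a clean run-in supports.** With 0 DLTs in 3, the exact one-sided 95% upper limit for the DLT rate is 1 − 0.05^(1/3) = 63.2%. With 0 in 6 it would be 1 − 0.05^(1/6) = 39.3%. Either limit applies only to the doses actually given.

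**5. Illustration with assumed DLT rates (none are in the documents).** Take clearance as 0 of 3, or 1 of 3 followed by 0 of 3. Its probability is (1−p)³ + 3p(1−p)⁵.
- p = 5%, assumed at 25 mg: 0.857 + 0.116 = 0.97.
- p = 40%, assumed at the RP2D in a deep lesion: 0.216 + 0.093 = 0.31.
- Over 2–10% at the low dose the range is 0.995 to 0.91. Over 30–50% at the RP2D it is 0.49 to 0.17.

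So if toxicity rises with dose, the result depends heavily on the doses given.

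**6. The protocol's own exposure margin.** Section 1.2 puts the 10 mg/kg IV monkey dose, used to cover worst-case systemic exposure, at 8 times the 25 mg starting dose. A 200 mg dose is 8 times 25 mg, so the margin falls to 8/8 = 1, and Section 7.2.1 calls the two equivalent. That monkey dose was well tolerated, so this shows no harm. It does show that 25 mg and 200 mg are not interchangeable.

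**7. The DLT period.** Section 3.1 needs DLTs assessed in six subjects after expansion. Section 3.1.1 attaches the Part 2 period to three. The contact rules in Sections 8.3 and 8.3.2 and the DLT definition in 8.3.3 all point to 3.1.1. Read literally, subjects 4 to 6 and later deep-lesion subjects fall outside the expansion rule and the contact rules. The accrual stop may be narrowed too, because it counts events that fit the DLT definition. The Synopsis and Section 3.1 indicate that this is not intended.

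**The case against.** The strongest reply is that the run-in tests the treatment Part 2 actually gives. Concentration is fixed and volume follows tumour size by design (Section 1.2), with the RP2D as a cap. Each total dose stays within one assessed in Part 1. This stands as a defence of the dosing scheme, but such a run-in supports deep-lesion dosing only at the doses given.

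A reader might infer that clearance is automatic on DLT counts. The documents do not support that. The Committee reviews all safety data (Sections 3.1, 9.7) and evaluates them after the 3 or 6 subjects (Section 8.3.2). The trial is open-label and the quantity used per subject is recorded (Section 6.6), so the Committee could consider dose. Continuation after 0 of 3 is implied rather than written. What remains is that nothing requires dose to be considered or a limit recorded.

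A reader might also infer that later deep-lesion subjects go unwatched. They do not. SAEs reach the sponsor within 24 hours, up to 90 days after the last dose or until new anticancer therapy, without exceptions (Sections 7.2.2, 7.2.4, 7.2.5.1). AEs are recorded to 30 days or new anticancer therapy, and data are reviewed continually. Lesions near major vessels or in other high-risk sites should not be injected (Section 3 footnote). These safeguards reduce the risk but are not tied to dose.

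Finally, volumes are set in an administration document that was not supplied and may make low doses unlikely. Deep-only subjects come mainly from one melanoma category (Section 4.1, criterion 4), so they may be few. Both points stand.

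**Conclusion.** The point holds as a gap in the written rule, conditional on an RP2D above 25 mg. The supplied text lets the run-in clear with 0 of 3 or 0 of 6 subjects at the RP2D in a deep lesion, at doses as low as 1/2, 1/4 or 1/8 of an RP2D of 50, 100 or 200 mg. The RP2D and the share of deep-lesion subjects are not given, so neither the likelihood of this nor the resulting risk can be quantified. The clearance probabilities above are illustrations only.

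It would be too strong to say that the run-in will be done at low doses, or that subjects are exposed to a shown hazard. The documents establish neither. The conclusion also depends on the administration document setting no rule that closes the gap.

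The narrow DLT period in Section 3.1.1 is a separate inconsistency with the Synopsis and Section 3.1. It needs correcting whatever the RP2D.

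**What to change.** 1. **Sections 3.1 and 8.3.2.** Give the Safety Committee the mg injected into deep lesions for each run-in subject, and have it record the highest deep-lesion dose its clearance supports. For doses split between deep and superficial lesions, capture mg per lesion.
2. **Section 3.1.1.** Apply the Cycle 1, Day 1 to 21 DLT period to all Part 2 subjects, as in the Synopsis, so that the expansion, 24-hour contact and >30% rules work for subjects 4 to 6 and later.
3. **First higher dose.** When a later subject first receives a deep-lesion dose above the recorded maximum, send that subject's Cycle 1 data to the Committee for ad-hoc review. If a DLT occurs, the Committee decides whether to cap the deep-lesion dose at the recorded maximum.
4. **Tables.** Show Part 2 DLTs and AEs by dose received and by deep versus superficial, as well as pooled. The Synopsis tabulates by dose level without saying where a Part 2 subject given less than the RP2D belongs. Section 8.2 lets a detailed SAP, not supplied, prevail, so the table may already be planned.

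**Cost.** Protocol wording, one table with small cells, and a few extra reviews. No review is needed if a run-in subject received the RP2D in a deep lesion. Otherwise the number depends on the volume steps used. If the whole run-in stayed at 1 mL and doses rose in whole-mL steps (an assumption), the maximum is 2−1 = 1, 4−1 = 3 or 8−1 = 7 reviews for an RP2D of 50, 100 or 200 mg. Half-mL steps to 8 mL would give 14. The count cannot exceed the number of later deep-lesion subjects.

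**Limit.** The recorded maximum states exposure; it does not show a low DLT rate. One subject without a DLT at that dose has an upper limit of 1 − 0.05 = 95%.

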# Concomitant Medications

All concomitant medications received from 30 days before the Screening visit through 30 days after Termination/ET visit should be recorded. Concomitant medications administered more than 30 days after Termination/ET visit should be recorded if they are part of an SAE's treatment.

Medications specifically prohibited in the Exclusion Criteria are not allowed during the study. If there is a clinical indication for any medication specifically prohibited during the study, the study continuation should be discussed with the Sponsor's Medical Monitor. The PI should discuss any questions regarding concomitant medications with the Sponsor's MM. The final decision on any supportive therapy rests with the PI and/or the subject's primary physician. However, the decision to continue the subject's participation in the study requires the mutual agreement between the PI, the Sponsor and the subject.

#### **Acceptable Concomitant Medications:**

All treatments that the PI considers necessary for the subject's welfare may be administered at the discretion of the PI in keeping with the acceptable standards of medical care. All concomitant medications, including their indication, will be recorded in the subject's medical file and on the eCRF including all prescription; over the counter (OTC), herbal supplements, and IV medications and fluids. If any change occurs during the study period, documentation of reason for change, drug dosage, frequency, route of administration and date should also be included in the subject's medical file and eCRF.

agalin A subsidiary of Bio	DINE X	PRIVILEGED & CONFIDENTIAL
Investigational Product: AGI-134		Protocol No. AGI-134.FIM.101
Phase: I/IIa	doses of AGI-134 in unresectable/metastatic solid tumours.	Version 6.1 31 May 2021

# **Concomitant Medications**

#### **Prohibited Concomitant Medications:**

Subjects are prohibited from receiving the following medications during the Core study, beginning at Screening visit until Termination visit (week 54) or disease progression, whichever comes first:

- Systemic glucocorticoids for any purpose other than to modulate an
  event of suspected immunologic aetiology or for systemic and local
  reactions secondary to the treatment. The use of physiologic doses of
  corticosteroids may be approved after consultation with the Sponsor.

   Note: Inhaled steroids are allowed for management of asthma, and
  dermatological formulations are allowed to reduce the intensity of
  injection-site reactions.
- Therapies for the disease under study:
  - Antineoplastic systemic chemotherapy or biological therapy
  - Immunotherapy or other therapy not specified in this protocol
  - Chemotherapy not specified in this protocol
  - Investigational agents other than AGI-134
  - Radiation therapy: localised radiation therapy may be considered on an exceptional case by case basis after consultation with the Sponsor.

During the Long-Term Follow-Up period, subjects who have no disease progression should be followed up until disease progression, new cancer treatment or withdraw consent. Subjects may receive other treatments following progression and/or upon investigator's and/or the subject's primary physician decision.

For subjects who, in the assessment of the PI, require the use of any of the aforementioned treatments for clinical management, the study continuation should be discussed with the Sponsor's Medical Monitor.

agalin A subsidiary of Bio	OLINE AX	PRIVILEGED & CONFIDENTIAL
Investigational Product: AGI-134	A Phase I/IIa, multicentre, two-parts, open label study designed to evaluate the safety and tolerability of escalating	Protocol No. AGI-134.FIM.101
Phase: I/IIa	doses of AGI-134 in unresectable/metastatic solid tumours.	Version 6.1 31 May 2021

# Study Primary Endpoint Endpoints To assess the safety and tolerability of AGI-134 injected intratumourally, as well as to determine the MTD and the RP2D. Secondary Endpoints To characterise the PK profile of AGI-134 To assess the immune response to AGI-134 and to support the To assess biomarkers that may serve as surrogate markers or predictors of clinical efficacy **Exploratory Endpoints**

agalin A subsidiary of Bio	OLINERX	PRIVILEGED & CONFIDENTIAL
Investigational Product: AGI-134	A Phase I/IIa, multicentre, two-parts, open label study designed to evaluate the safety and tolerability of escalating	Protocol No. AGI-134.FIM.101
Phase: I/IIa	doses of AGI-134 in unresectable/metastatic solid tumours.	Version 6.1 31 May 2021

